### RCT:

## Life Care Specialist (LCS) - Pain management and prevention of substance misuse

#### Emory University Department of Orthopaedic Surgery

#### **Introduction and Background:**

Opioids are psychoactive substances (narcotics) primarily used for pain relief by producing euphoric effects. Although regularly prescribed by physicians, opioids are highly addictive. Examples include, but are not limited to, morphine, codeine, and oxycodone. Opioids block feelings of pain and trigger a release of dopamine. Dependence occurs with repeated use, as the parts of the brain naturally responsible for releasing dopamine rely on the drug for proper function. When avoided, patients can quickly experience severe withdrawal symptoms similar to the flu.

In the United States, more than 115 people die from opioid overdose every day. Despite a year-over-year increase in opioid overdose deaths since the year 2000, opioids remain among the most effective medications providers can offer to control pain. In 2019, the Centers for Disease Control and Prevention (CDC) was granted 475 million research dollars for opioid overdose prevention and surveillance. Reducing dependence upon opioids has become a national priority. Evidence has shown that while prescription of analgesic opioids has declined, it has come at the expense of effective pain control. This is particularly true in the field of orthopaedic trauma where pain management continues to be centered around opioid pharmaceutical analgesia. Trauma patients are more likely than other types of patients to be under the influence of psychoactive drugs and alcohol use. The strongest risk factor for developing opioid use disorder is pre-existing substance use disorder. Risk factors for opioid overdose mortality include: middle age, history of substance abuse, including prescription and illicit drugs and alcohol, comorbid mental and medical condition, methadone use, unemployment, polysubstance abuse, opioid naivety, sleep apnea, and pain intensity; these are all conditions representative of typical U.S. trauma patient populations. This significant overlap places high importance on implementing alternative solutions to pain management

within this population, and aligns with the CDC NCICP research priority alignment to develop and evaluate an innovative prevention strategy to prevent overdose, including those at greatest risk.

Addiction treatment costs near \$78.5 billion and rising, less than 10% of people in need receive treatment.

According to studies of patients discharged from the hospital after being prescribed a new medication:

- 86% were aware that they had been prescribed new medications.
- Fewer could identify the name (64%) or number (74%) of their new medications of their dosages (56%), the schedule to take them (68%), or the purpose of the prescription (64%.)
- Only 22% could name at least one adverse effect.
- Only 11% could recall being told of any adverse effects.

Further, orthopaedic surgeons are the third-most frequent providers of opioid prescription medications among physicians, and orthopaedic surgical patients are at the highest risk of chronic postoperative opioid use. Orthopaedic trauma surgeons face a very difficult task in managing acute pain and the consequences associated with over-prescription of opioid analgesics. Most patients with orthopaedic trauma injuries have very painful injuries and need appropriate pain control. What we largely fail to understand as providers and then fail to convey to patients is that opioid dependence exists on a continuum: from pain-related appropriate use to dependence – and that addiction can happen to anyone holding a prescription. Orthopaedic trauma surgeons have very little training in acute pain management, yet are treating the highest risk patients with opioids every single day.

Within the orthopaedic trauma population at Grady, 20% of patients report a history of substance abuse, 30% have previously used opioid medications for pain, and nearly 25% report taking opioid pain medications up to 1 year after their trauma (*[name] et al. manuscript in preparation*). Trauma patients are particularly at high risk.

In pediatrics, there is evidence that non-pharmacological interventions by Certified Child Life Specialists (CCLS) has led to more cooperation, reduction in perceived pain, and higher satisfaction scores. The use of CCLS in children who suffer from orthopaedic trauma is associated with fewer opioid prescriptions.

The Christopher Wolf Crusade (CWC) is a 501C3 non-profit providing preventative solutions, education, and advocacy for the American opioid epidemic. Founded by [name] in 2018, CWC is on a mission to save lives worldwide.

CWC proposes to introduce a Life Care Specialist (LCS) as an integral member of the clinical team, with a focus on "pain coaching" for trauma patients. In an analogous role served by CCLS in pediatrics, the LCS will introduce orthopaedic trauma patients to non-pharmacologic coping strategies for pain. Further, they will provide much needed patient-centric education on individualized risk for opioid misuse, as well as overdose prevention and safe disposal of unused opioids.

CWC's primary focus is to introduce a behavior-specific intervention at the time of inpatient hospitalization for trauma to decrease overall opioid utilization and improve pain control in the post-trauma time period. We are collaborating with key stakeholders in the opioid epidemic to develop an official pain management protocol, as well as conducting an introductory study for a new field of Pain Management. The goal is to see Life Care Specialists (LCS) staffed in hospitals to focus on pain management and addiction prevention for patients. The LCS position does not currently exist in the healthcare field. The LCS is a behavior-based pain "coach" who educates patients on risks of opioid dependence and offers non-traditional non-pharmacologic options for pain control. In addition, the LCS will act as a liaison between the patient and

the physician – to ensure that traditional pharmacologic-based pain control regimens are optimized. Current post-operative protocols for pain management in trauma are very opioid-based. They lack multimodal non-opioid based pharmacologic options and they have no non-pharmacologic behavioral-based component.

All LCS involved in the research study will become certified as a teacher of the Community Resiliency Model (CRM). CRM is an evidence-based model of wellbeing created by Elaine Miller-Karas of the Trauma Resource Institute.

LCS Role and Responsibilities will be overseen by CWC:

- The LCS will provide patients with individualized risk assessment for opioid misuse.
- LCS will act as patient's "Pain Coach." Providing targeted education and behavior-based pain treatment options.
- LCS will train and provide CWC evidence based non-pharmaceutical pain management techniques, using the Community Resiliency Model.
- The LCS will use the Opioid Risk Tool (ORT) as the method to identity the risk of substance misuse.
- LCS will provide education, support and resources.
- The LCS will provide local, state, and national resources to enhance the whole health aspect of the position. These resources include but are not limited to: written documents that outline the key concepts of the pain management techniques taught by the LCS and a list of hotlines and websites.
- LCS, when applicable, will provide education for caretakers on the risk of opioid use and the non-pharmaceutical pain management protocol.
- LCS will provide follow up for all patients in intervention group.

#### **Objectives:**

The overall hypothesis of this pilot randomized-controlled trial is that the introduction of an LCS as a novel member of the clinical care team will help reduce opioid utilization, decrease pain scores, and improve patient understanding of their addiction risk in the aftermath of orthopaedic trauma.

The first aim will evaluate the effectiveness of LCS intervention on pain control and opioid utilization; the second aim will evaluate the effectiveness of LCS intervention on the patient perspective and understanding of their risks; and the final aim will provide early evidence into which patients benefit most from LCS intervention.

All patients will be assessed with a comprehensive social determinants of health survey at the beginning of the study, and follow-up assessments will include actual morphine equivalents utilized (inpatient and outpatient), pain scores (inpatient and outpatient), and substance use surveys up to 1-year post-trauma.

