#### **Study design and methods:**

The pilot trial will include 200 patients – 100 randomized into LCS intervention. Prior to randomization, all patients will be given a standardized, validated, comprehensive social determinants of health assessment.

Patients will be randomized to either:

(1) LCS intervention - With *Opioid Risk Education*, patients will receive opioid education after completing the validated Opioid Risk Tool (ORT), a detailed substance abuse survey and mental health screening, and Naloxone education. *Therapeutic Intervention* will include the Community Resiliency Model CRM), progressive muscle relaxation, sound therapy. *Clinical Pain Coordination* will include directed referrals for complex needs, including mental health and substance use

- disorders, as needed. In addition to above mentioned 3 intervention components, all patients in the LCS intervention arm will also receive the current standard-of-care.
- **(2) No LCS intervention -** Patients will receive the current standard-of-care for pain management in the aftermath of trauma, which includes: a standardized prescription protocol, hospital-system approved discharge instructions which provide written instruction on how to taper opioid use, links to written/online resources for opioid misuse, overdose prevention, and State-approved disposal options.

Patients will be monitored throughout the course of the 1-year study for outcomes. They will also have the same quantity and quality of interaction with their usual clinical providers (orthopaedic trauma surgeon, physician's assistant).

This pilot trial will provide information on the effectiveness of LCS for pain intervention, as well as on study design, retention, effect sizes, and outcomes assessment. Our long-term goals are to determine whether LCSs are beneficial for decreasing opioid risk and improving pain management, and if so identify (1) the key effectiveness factors to the LCS intervention, (2) whether the LCS intervention can decrease overdose-related deaths, and (3) how to scale this model nationally, similar to the Child Life Specialist model.

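### The Objectives promise 1-year surveys and two aims that the schedule and Statistical Analysis do not carry through; data end at 3 months, and post hoc power cannot show who benefits

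*Combined protocol and SAP*

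**What the plan says.** **Horizon.** The Objectives include "substance use surveys up to 1-year post-trauma". Study design and methods adds: "Patients will be monitored throughout the course of the 1-year study for outcomes". Study Procedures/Assessments schedules follow-up at 2 weeks, 6 weeks and 3 months. The record review of morphine equivalents (Inpatient Pain and Opioid utilization) goes up to 3 months. The Visit Schedule has four visits, the last at 3 months. Aim 2 of the Statistical Analysis models opioid use up to 3 months and calls it long-term.

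**Aims.** The first aim in the Objectives is pain control and opioid use. The next is worded as follows: "the second aim will evaluate the effectiveness of LCS intervention on the patient perspective and understanding of their risks". A third, which concerns variation in benefit between patients, reads: "the final aim will provide early evidence into which patients benefit most from LCS intervention". The overall hypothesis also expects the intervention to "improve patient understanding of their addiction risk in the aftermath of orthopaedic trauma". The three aims in the Statistical Analysis are patient-reported pain outcomes, opioid use, and actigraphy feasibility.

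**Measures that bear on the unmatched aims.** The OLT covers knowledge of opioid risk and is scheduled at Visit 1 and at 3 months; the Statistical Analysis does not name it. The Patient Satisfaction Survey section says satisfaction will be compared between arms. On subgroups, the Power paragraph says only that post hoc power analyses will accompany exploration of outcome differences by demographics, with gender as the example.

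**The concern.** Someone reading the Objectives would expect substance-use data to 1 year. The Introduction motivates the trial with the finding that "nearly 25% report taking opioid pain medications up to 1 year after their trauma", and data that stop at 3 months cannot address use at that distance. Calling a 3-month outcome long-term adds to the risk of over-reading.

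Two of the three stated aims have no analysis aim. Understanding of risk is one of three elements of the overall hypothesis, yet no contrast is set for the instrument that measures it. For who benefits, the planned exploration concerns a different quantity: whether men and women differ in outcome is not whether the intervention works differently in men and women. The pilot is meant to give early evidence and effect sizes, and post hoc power provides neither an estimate nor an interval for a difference in effect.

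**Working it through.** **1. Horizon, section by section**

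| Section | Last time point |
|---|---|
| Objectives (substance use surveys) | 1 year post-trauma |
| Study Procedures/Assessments (visits) | 3 months |
| Inpatient Pain and Opioid utilization (record review) | 3 months |
| Visit Schedule (PMQ, PDUQ, PROMIS misuse) | Visit 4, 3 months ± 14 days |
| Statistical Analysis, Aim 2 (opioid models) | 3 months |

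The schedule covers 3 of the 12 months. The Objectives count time from the trauma, so this is patient time, and no substance-use measure is scheduled after Visit 4.

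**2. Aims side by side**

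| Objectives | Statistical Analysis |
|---|---|
| Pain control and opioid use | Aim 1 (pain, PROMIS) and Aim 2 (opioid use) |
| Patient perspective and understanding of risk | No aim; satisfaction comparison stated elsewhere, OLT not mentioned |
| Who benefits most | No aim; post hoc power sentence only |
| Not listed | Aim 3, actigraphy feasibility |

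The LASSO step in Aim 1 selects adjustment covariates. No arm-by-moderator term is specified.

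**3. The plan's own power figure.** Inputs: 200 patients, 100 of them randomised to the intervention (Study design and methods); 85% power, alpha 0.05 and a 0.5-point difference (Power). The 85% cannot be reproduced, because no SD, within-patient correlation or number of measures is given, and sidedness is not stated. Taken at face value, it implies:

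- Two-sided: SE = 0.5/(1.960 + 1.036) = 0.167; 95% CI half-width 1.96 × 0.167 = 0.33; effective SD 0.167/√(2/100) = 1.18.
- One-sided: SE = 0.5/(1.645 + 1.036) = 0.186; half-width 0.37; effective SD 1.32.

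**4. Precision of an arm-by-moderator interaction.** With a share p of patients in the smaller subgroup, equal variances and subgroups balanced across arms, SE(interaction) = SE(main) × 1/√(p(1−p)). The multiplier is 2.0 at p = 0.5 and 2.5 at p = 0.2. The 20/80 case corresponds to the Introduction's statement that "20% of patients report a history of substance abuse". The gender split is not given.

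| Basis | Main effect half-width | 50/50 | 20/80 |
|---|---|---|---|
| 85% power, two-sided | 0.33 | 0.65 | 0.82 |
| 85% power, one-sided | 0.37 | 0.73 | 0.91 |
| Assumed SD 2.0, correlation 0.5, three measures | 0.45 | 0.91 | 1.13 |

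In the last row the effective SD is 2.0 × √((1 + 2 × 0.5)/3) = 1.63, and power for a 0.5-point main effect would be 58%, not 85%. On the two-sided basis, power for a 0.5-point interaction is Φ(0.5/0.334 − 1.96) = 32% at 50/50 and Φ(0.5/0.417 − 1.96) = 22% at 20/80.

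**5. Post hoc power.** If it is computed from the observed effect, it equals Φ(z − 1.96) + Φ(−z − 1.96), where z is the normal quantile at 1 − p/2 and p is here the two-sided p-value. So p = 0.05 always gives 50% and p = 0.30 always gives 18%. It adds nothing to the p-value.

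**6. How many interactions.** Two moderators in the pain-score model and the follow-up MME/day model give 2 × 2 = 4. Applied to every Aim 1 and Aim 2 model (one NRS, three or four PROMIS scales, two MME), the count is 2 × (1 + 3 + 2) = 12 to 2 × (1 + 4 + 2) = 14.

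**The case against.** **It is a pilot and the data are collected.** True: the OLT is scheduled, satisfaction is to be compared between arms, and demographic differences are to be explored. A reader might infer that risk understanding goes unmeasured or that subgroups are ignored, and the documents do not support either. What is absent is an analysis aim and an estimate of effect modification.

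**The 1-year conflict may be smaller than it looks.** A reader might take the 1-year study in Study design and methods as proof of 1-year follow-up per patient. It may mean the duration of the study. The compensation list also ends at 3 months, but it omits the scheduled 6-week visit, so it says little about the horizon. The conflict rests on the Objectives against the visits, record review, visit table and models. The documents do not say which side is out of date.

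**The precision figures lean on an unverifiable input.** This stands. They are conditional on the 85% and on sidedness, hence the range. The direction, low precision, holds in every row.

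**Post hoc power is not defined in the plan.** Also fair: a detectable-difference calculation would not simply restate the p-value. It would still not estimate a difference in treatment effect.

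**OLT scoring.** The response scale runs from 1 (definitely true) to 7 (definitely false), and higher totals are said to mean better literacy. A reader might infer a scoring error. The items are not in the documents, and the rule works if all the statements are false or the true ones are reverse-scored. This is a query only.

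**Conclusion.** The point holds on the text. The Objectives state a 1-year horizon for substance use surveys, and nothing is scheduled after 3 months. Two of the three aims in the Objectives have no matching analysis aim. The only subgroup provision does not address who benefits.

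An interaction estimate from scheduled data would have a 95% CI half-width of about 0.65 to 0.82 pain points (two-sided alpha) or 0.73 to 0.91 (one-sided), against the 0.5-point difference used to size the trial. These figures assume that the 85% power is right, variances are equal, subgroups are balanced across arms and dropout is nil; a larger SD widens them.

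A reader might infer that the main pain and opioid comparisons are undermined. They are not: both have analysis aims and data to 3 months. The defect lies in the claimed duration and in the two unmatched aims.

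**What to change.** 1. **Horizon.** State outcomes to 3 months in the Objectives, Study design and methods, and Aim 2, and limit conclusions to 3 months, unless 1-year surveys are actually scheduled.
2. **Who benefits.** Replace post hoc power with arm-by-moderator interaction estimates and 95% CIs, labelled exploratory and without significance claims. Fix a short moderator list: gender, which the plan names, and for example prior substance use from the social determinants survey if that is taken before randomisation. Restrict this to the pain-score and follow-up MME/day models, about 4 interactions. Keep arm, moderator and their product out of LASSO selection, and state that precision is low.
3. **Aims.** Use one list in the Objectives and the Statistical Analysis. Include a between-arm comparison of the 3-month OLT with a 95% CI, adjusted for Visit 1 OLT only if that is taken before allocation or any contact with the specialist. Keep the stated satisfaction comparison, and show actigraphy feasibility in the same list.
4. **Queries, not errors.** Confirm the OLT scoring direction. Make the sections agree on which measures precede allocation: Study design and methods says "Prior to randomization, all patients will be given a standardized, validated, comprehensive social determinants of health assessment", while Study Procedures/Assessments gives the battery of measures after allocation.

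The cost is wording, one OLT comparison and about four interaction terms, all on scheduled data. Adjusting for Visit 1 OLT would require that measure to come early enough; the unadjusted comparison would not. The downside is a narrower claim about duration and wide exploratory intervals.

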#### **Study design and methods:**

The pilot trial will include 200 patients – 100 randomized into LCS intervention. Prior to randomization, all patients will be given a standardized, validated, comprehensive social determinants of health assessment.

Patients will be randomized to either:

(1) LCS intervention - With *Opioid Risk Education*, patients will receive opioid education after completing the validated Opioid Risk Tool (ORT), a detailed substance abuse survey and mental health screening, and Naloxone education. *Therapeutic Intervention* will include the Community Resiliency Model CRM), progressive muscle relaxation, sound therapy. *Clinical Pain Coordination* will include directed referrals for complex needs, including mental health and substance use

- disorders, as needed. In addition to above mentioned 3 intervention components, all patients in the LCS intervention arm will also receive the current standard-of-care.
- **(2) No LCS intervention -** Patients will receive the current standard-of-care for pain management in the aftermath of trauma, which includes: a standardized prescription protocol, hospital-system approved discharge instructions which provide written instruction on how to taper opioid use, links to written/online resources for opioid misuse, overdose prevention, and State-approved disposal options.

Patients will be monitored throughout the course of the 1-year study for outcomes. They will also have the same quantity and quality of interaction with their usual clinical providers (orthopaedic trauma surgeon, physician's assistant).

This pilot trial will provide information on the effectiveness of LCS for pain intervention, as well as on study design, retention, effect sizes, and outcomes assessment. Our long-term goals are to determine whether LCSs are beneficial for decreasing opioid risk and improving pain management, and if so identify (1) the key effectiveness factors to the LCS intervention, (2) whether the LCS intervention can decrease overdose-related deaths, and (3) how to scale this model nationally, similar to the Child Life Specialist model.

#### **Study Procedures/Assessments:**

Potential patients will be identified during the daily orthopaedic trauma morning report. Eligibility will be determined by the clinical research coordinator (CRC).

If the patient meets inclusion criteria, he/she will be approached by the CRC, and if informed consent is obtained, they will be enrolled into RedCAP for randomization into Group 1 (non- LCS) or Group 2 (LCS). After consenting, enrolling, and allocation, research staff will administer a battery of measures on tablets stored in RedCap, or on paper and later transcribed into REDCap to all participants (See Table).

Each day throughout hospitalization, the average pain score over the past 24-hours will be recorded via the nursing staff. During their follow up visits with the surgical team at Grady Hospital scheduled at 2-weeks, 6-weeks, and 3-months postoperatively participants will again be provided a tablet to complete outcome measures. In the event participants cannot physically travel to the clinic, appointments will be conducted over video conferencing and participants will have the option to be emailed the outcome measures to complete. If they are unable to complete the measures via email within 72-hours study staff will call participants to complete measures over the phone. If no response, paper copies of the measures will be mailed to participants with prepaid postage to return them.

The following data will be collected on the patients:

- Demographics:
  - Name, date of birth, date of admission, gender, ethnicity, body mass index.
- Trauma registry data:
  - Data abstraction that is completed by a separate quality team contained within the trauma department. i.e., injury severity score, mechanism, drug screen on arrival, alcohol screen, pre-existing conditions, inpatient complications.
- Comprehensive social determinants of health (SDOH) survey:
  - Includes assessments of: housing, financial stability, education, community context, intimate partner violence, health literacy, prior personal and family substance use, a validated measure of post-traumatic stress disorder, adverse childhood experiences, and mental illness. This has been utilized in prior research by this team and takes approximately 20-25 minutes to complete (attached).

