#### VISIT SCHEDULE AND ASSESSMENTS

Assessment	Visit 1:	Visit 2:	Visit 3:	Visit 4:
	Inpatient	2 Weeks (±	6 Weeks (±	3 Months (±
	Hospitalization	7 days)	14 days)	14 days)
Demographics	X			
Trauma registry data	X			
Comprehensive Social Determinants of Health (SDOH) Survey	X			
Revised Opioid Risk Tool (ORT)	X			
Short Form 36 Health Survey Questionnaire (SF-36)	X			X
Pain Management Questionnaire (PMQ)	X	X	X	X
Prescription Drug Use Questionnaire (PDUQ)	X	X	X	X
PTSD Screener	X			X
PROMIS: Sleep Disturbance	X	X	X	X
PROMIS: Physical Function	X	X	X	X
PROMIS: Pain Interference	X	X	X	X
PROMIS: Prescription Pain				X
Medication Misuse				
Opioid Literacy Tool (OLT)	X			X
Patient Satisfaction Survey		X		
Naloxone Questionnaire		X	X	X
PAC-SYM	X	X	X	
Inpatient Opioid Utilization (MME/day)	X			
Inpatient Numerical Rating Scale (NRS) Pain Score	X	X	X	X
Medication Electronic Monitoring (MEMS) devices:		X	X	X
Defense and Veterans Pain Rating Scale (DVPRS)	X	X	X	X

Inpatient Sleep Actigraphy	X				l
Field notes and participant quotes	X	X	X	X	l
Participant Compensation	X	X		X	ı

Questionnaires/surveys and meetings with the Life Care Specialist will occur during scheduled telehealth appointments. No charges will be generated specifically relating to the research components.

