#### **Statistical Analysis:**

**Aim 1:** Examine differences in post-surgical patient-reported pain related outcomes between those in the intervention compared to the control arm. A multivariable mixed effects logistic regression model will be constructed to test the hypothesis that participants in the intervention arm have lower average NRS pain scores and PROMIS scores postoperatively compared to participants in the control arm. A separate linear mixed effects model will be constructed for each outcome. This modeling approach will enable the team to examine the mean differences in each patient-reported pain related outcome while adjusting for covariates (e.g., mental health history, BMI, surgery type, etc.).  The mixed effects modeling will account for potential collinearity between participants seen by the same surgeon by fitting a random effect for both factors. Models will be constructed using a Least Absolute Shrinkage and Selection Operator (LASSO) method. 50,51 An extension of traditional ordinary least squares regression model building, LASSO is a machine learning method capable of balancing bias and variance to build the most predictive model with a large subset of covarying factors using a penalized approach. A LASSO approach enables the team to systematically evaluate the variance introduced into regression modeling by hundreds of potential confounders. This unique quantitative capability will allow the research team to exploit the hundreds of data points collected from the electronic health records and the patient-reported outcomes collected per participant. The inclusion of these longitudinal measures makes it feasible to reduce statistical variation in the mixed effects models over time and therefore isolate the effect of the intervention. The fit of the most appropriate and still parsimonious model produced by the LASSO will be assessed based on the AIC score.

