Aim 2: Evaluate the effectiveness of Life Care Specialist intervention on reducing long-term postoperative opioid medication utilization. As described above, a systematic machine learning guided model construction approach will be used to also test the working hypothesis that participants in the intervention will report decreased utilization of opioid pain medications both in the inpatient and outpatient setting up to 3-months postoperatively. Separate mixed-effects models will be constructed to estimate differences in average MME/day during inpatient hospitalization as well as to estimate difference in average MME/day over every study follow up point up to 3-months postoperatively.

Aim 3: Explore the feasibility of utilizing actigraphy devices to capture postoperative functional outcomes among patients during their hospitalization and up to 2-weeks postoperatively following orthopaedic trauma. Generalized estimating equations (GEE) will be used to explore changes in functional outcomes over the 2-

week postoperative period. For example, activity will be measured as average step per day and sleep will be measured as average nightly sleep efficiency and duration. Separate GEE will be computed for each actigraphy related measure. In the event a significant change in any of the objective outcomes, a linear mixed-effect model will be constructed to ascertain any significant differences in actigraphy collected outcomes exist between participants in the intervention and the control arms over the two-week postoperative period.

Power: A sample of 200 provides 85% power ( $\alpha$ =0.05) to detect a difference as small as 0.5 in the mean pain score between the intervention arm and the controls using repeated measures mixed effects modeling (Power Analysis and Sample Size Software, NCSS, Kaysville, UT, USA). All analyses will be conducted in R (R Core Team, Vienna, Austria) by the Co-PI and his team at the Nell Hodgson Woodruff School of Nursing ([name]). The *glmnet* package will be used to determine which variables should be included in the regression models using a LASSO approach, the *lme4* package will be employed to compute final regressions and assess fit. Post hoc power analyses will be conducted when exploring differences in outcomes based on demographics (e.g., gender).

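### The plan gives two orders for the SDOH survey and randomisation, puts the first self-reports after allocation, and does not limit LASSO covariates to pre-randomisation values

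*Combined protocol and SAP*

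**What the plan says.** Study design and methods states: "Prior to randomization, all patients will be given a standardized, validated, comprehensive social determinants of health assessment".

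Study Procedures/Assessments gives a different sequence. The coordinator obtains consent, the patient is enrolled in REDCap for randomisation, and then: "After consenting, enrolling, and allocation, research staff will administer a battery of measures on tablets stored in RedCap", or on paper, to all participants, with a reference to the table. The visit table lists "Comprehensive Social Determinants of Health (SDOH) Survey" at Visit 1 and has no pre-randomisation column. Objectives says only that the survey comes at the start of the study.

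For the Life Care Specialist (LCS) arm, Study design and methods says that "patients will receive opioid education after completing the validated Opioid Risk Tool (ORT", and the same sentence goes on to a substance abuse survey, mental health screening and naloxone education.

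Under Statistical Analysis, Aim 1 tests whether "participants in the intervention arm have lower average NRS pain scores and PROMIS scores postoperatively compared to participants in the control arm". Its LASSO is meant to "exploit the hundreds of data points collected from the electronic health records and the patient-reported outcomes collected per participant", and the section adds: "The inclusion of these longitudinal measures makes it feasible to reduce statistical variation in the mixed effects models over time". In the Power paragraph, the glmnet "package will be used to determine which variables should be included in the regression models using a LASSO approach".

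**The concern.** There are two linked problems.

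- **Order.** Staff cannot follow both sections for the SDOH survey. For the first administration of the ORT, SF-36, PMQ, PDUQ, PTSD screener, three PROMIS scales, OLT, PAC-SYM and DVPRS there is no contradiction, but the only stated order is after allocation. The plan describes no blinding, and a patient who knows that a pain and opioid-misuse coach has been assigned might answer differently, in either direction.
- **Covariates.** Nothing limits the LASSO candidates to values collected before randomisation. PROMIS is both an Aim 1 outcome and a Visit 1 measure, so its Visit 1 score is a natural candidate. Follow-up scores, which the intervention itself may change, are not excluded either.

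Adjusting for a variable that allocation has moved can bias the estimated arm effect. Visit 1 scores used as a reference for change (the SF-36 is included to capture change) or to define who benefits most (the final aim in Objectives) would be exposed too, although Statistical Analysis specifies no analysis that uses them so.

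**Working it through.** **Text check.**

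| Item | Study design and methods | Study Procedures/Assessments with visit table |
|---|---|---|
| SDOH survey | before randomisation | battery after allocation; Visit 1 |
| ORT | before LCS education, but described within the randomised arm | after allocation; Visit 1 only |
| Other Visit 1 self-reports | none ordered by name against allocation | after allocation; Visit 1 and again later |

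Among the questionnaires, only the SDOH survey and the ORT are confined to Visit 1. On a natural reading, the substance abuse survey and mental health screening also precede LCS education, but again after allocation. The note under the visit table puts questionnaires and LCS meetings in telehealth appointments without giving a sequence.

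**Size.** The documents give no figure to reproduce on this point; the stated 85% power is not involved. Every value of s, b and p below is an assumption.

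- s: the shift in a Visit 1 PROMIS score caused by allocation, 0.5 to 1 T-score points.
- b: the coefficient of that score in the outcome model, 0.3 to 0.7.
- p: the fraction of a reporting shift that carries over to follow-up, 0 or 1.

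Error without adjustment = p × s. Error with adjustment = (p − b) × s.

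| p | s | Unadjusted | Adjusted, b = 0.3 | Adjusted, b = 0.7 |
|---|---|---|---|---|
| 0 | 0.5 | 0 | −0.15 | −0.35 |
| 0 | 1 | 0 | −0.30 | −0.70 |
| 1 | 0.5 | 0.50 | 0.35 | 0.15 |
| 1 | 1 | 1.00 | 0.70 | 0.30 |

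With no carry-over, adjustment introduces an error of size b × s, between 0.15 and 0.70 points, whose sign depends on the direction of the shift. With full carry-over the unadjusted comparison is itself off by s, and adjustment reduces the error. With no shift, both errors are zero.

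**Scale.** Take SD 10 (the PROMIS norm in the protocol), 100 per arm, three follow-ups, no dropout and equal correlations between visits, so that b equals the correlation. Then SE = √((2/100) × 10² × [(1 + 2b)/3 − b²]).

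- b = 0.3: √(2 × 0.4433) = 0.94
- b = 0.7: √(2 × 0.31) = 0.79

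The no-carry-over errors therefore run from 0.15/0.94 = 0.16 to 0.70/0.79 = 0.89 standard errors.

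**The case against.** The strongest reply is that nothing shows any Visit 1 answer to be affected. The documents do not say that patients know their arm or have met the LCS when they complete the battery. Some assessments precede LCS education. PROMIS Sleep Disturbance and Pain Interference ask about the past seven days, so an early inpatient answer largely describes time before allocation. Many SDOH items are historical facts. The power statement concerns the mean pain score, and inpatient pain scores and opioid use come from the health record, outside the battery. The covariates named for Aim 1 are mental health history, BMI and surgery type. Visit 1 PROMIS is not named, and could instead enter the model as a repeated response. Finally, a persistent reporting shift would make adjustment helpful.

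Most of this stands, and it limits the point. A reader might infer that the baseline data are contaminated, that the arm comparison is biased, or that the plan commits to adjusting for post-allocation scores. The documents support none of these: they show an unprotected order and an open candidate list. Nor does the SDOH contradiction extend to the whole battery, because no other measure is given two conflicting positions relative to randomisation.

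The reply does not remove the conflict. The only reconciling reading is that the SDOH survey lies outside the battery, and no section says so. Nor does it supply the missing restriction on covariates.

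**Conclusion.** The point holds in this form, and should be fixed. The SDOH conflict is plain on the text, and so is the absence of a pre-randomisation limit on LASSO covariates. Together they mean that staff and analysts who follow the plan as written could adjust the arm effect for values recorded after allocation.

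Whether bias would follow is uncertain, and its size cannot be derived from the documents. The range of 0.15 to 0.70 T-score points rests on assumed shifts and coefficients and on no carry-over to follow-up. It is small at the low end, and with carry-over the net error differs. That unadjusted comparisons are safe is likewise true only if any reporting shift does not persist. The case for change rests on the contradiction and the low cost of removing the risk.

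**What to change.** 1. Edit Study design and methods and Study Procedures/Assessments to one order: consent; Visit 1 self-reports, including the SDOH survey and the ORT; randomisation; first LCS contact.
2. Add a REDCap confirmation, before randomisation, that the tablet forms are complete or that staff have checked the paper forms.
3. Align the LCS role list in Introduction and Background, which has the LCS use the ORT, so that the LCS works from the ORT result already collected.
4. In Statistical Analysis, limit LASSO covariates, and any change references or subgroup definers, to values collected before randomisation or fixed characteristics that allocation cannot change (for example age, injury type or arrival drug screen). This bars follow-up scores.
5. Treat any form completed late despite the check as a missing baseline, under one pre-stated rule that ignores arm and outcome, such as imputing the pooled mean.

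No items are added, since all participants already complete the battery. The cost is time before randomisation. The SDOH survey takes 20 to 25 minutes. The forms with item counts in the protocol add 36 (SF-36) + 26 (PMQ) + 9 (ORT) + 5 (PTSD screener) + 12 (three PROMIS forms) + 8 (OLT) + 12 (PAC-SYM) = 108 items. At an assumed 5 to 15 seconds each that is 9 to 27 minutes, so about 29 to 52 minutes in all, before the PDUQ and DVPRS. Some patients may be lost before randomisation, in unknown number. That would mean more consents to reach 200, but it would not bias the arm comparison.
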